91 largely been ignored by the literature. Due to the magnitude of the problem of obesity,
92 and the potential benefits of exercise with this population, it is important to determine the
93 elements of a feasible and effective physical activity program.

94

95 **SPECIFIC AIMS AND SCOPE OF THE PROPOSED RESEARCH**

96 The proposed research is a collaborative study involving the Eastern Maine Medical
97 Center Weight Management Program. This program currently has no formal physical
98 activity recommendation for its non-surgical participants. The Weight Management
99 Program managers are seeking guidance as to successful physical activity
100 recommendations for their patients. It is anticipated that a wide demographic will be
101 represented allowing the results to be applied across the spectrum of age and gender.

102 Objectives:

103 1. Identify any difference in the functional outcome measures resulting from
104 participation in the different forms of physical activity

105 2. Identify differences in compliance among the various types of physical activity with
106 the supervised group and individual sessions.
107 3. Determine the impact of the type of physical activity on the health measures
108 collected including blood pressure, and weight.
109 4. Identify differences in self-reported quality of life measures resulting from
110 participation in the different physical activities.

111

112

113 Clearly, an intervention that would reduce mobility deficits in this population and
114 improve overall health could have a tremendous impact on quality of life for a large
115 portion of the population. The overarching aim of the proposed study is thus to help
116 identify a beneficial and feasible program to impact activity level and therefore health
117 and well-being of people with morbid obesity.

118 **PARTICIPANT RECRUITMENT AND SELECTION:** Participants will be recruited from the Eastern
119 Maine Medical Center Weight Management practice in Bangor, Maine. The anticipated number
120 of participants will be 45 with 15 participants in each of 3 groups. Adult clients will be included
121 if they are at least 21 years old with no restriction on upper age range. Male and female clients
122 will both be included. Inclusion criteria are as follows: Body mass index (BMI) greater than 40,
123 as determined by the physician's office, and successful performance on the Four Square Step

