124 Test balance assessment at pre-screening to determine falls risk (described below), and the
125 ability to walk independently (with or without an assistive device) for at least 50 feet.
126 Participants must also be able to attend at least one supervised session at Husson University per
127 week for 8 weeks. Data will be included in our analysis if a person has attended at least half of
128 the supervised sessions. Exclusion criteria include: history of bariatric surgery; history of
129 neurological condition (stroke, brain injury, etc.); high fall risk (as indicated by pre-screening);
130 absence of medical clearance received from the physician's office; inability to consistently
131 attend exercise sessions; and pregnancy.

132 **LOCATION:** Participants will continue to attend routine physician appointments while enrolled
133 in the Weight Management Program at Eastern Maine Medical Center during the study for
134 medical monitoring and diet consultation. The proposed study does not modify any interaction
135 with the patient's current medical management. The Tai Chi and General Exercise groups will
136 meet once a week for 8 weeks at the Kenduskeag Laboratory on the campus of Husson
137 University in Bangor, Maine, along with 2 additional sessions for pre and post testing.
138 Participants will perform the exercises or Tai Chi forms at their homes or at another location of
139 their choice 2 additional times per week. Participants in the control group will also attend 2
140 sessions at the Kenduskeag Laboratory for pre- and post-testing; the remainder of their
141 participation will occur at a location of their choice. Functional outcome data, anthropometric
142 measures, height, weight, and vital signs will also be collected at the Kenduskeag Laboratory.

143 **DURATION:** The supervised exercise sessions will take place for 8 consecutive weeks.
144 Following the 8-week intervention, the participants will return for reassessment of the outcome
145 measures; thus each participant's time involvement in this study will be approximately 10 weeks
146 (including pre and post testing). We anticipate that this study will be done in two consecutive
147 phases, each spanning approximately one academic year, with the entire study taking place
148 between August of 2016 and May of 2018. The first phase of the study will include participants
149 who are in the Tai Chi group and a control group, and the other phase will include those who are

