202 rises is recorded. Lastly, the researchers will ask the participants to walk down a Zeno walkway,
203 which is an instrumented 20-foot pad that records gait parameters electronically. The

204 researchers performing the outcome measures data collection will be blinded to the group
205 assignment of the participants.

206 The groups of participants will include two intervention groups and two corresponding control
207 groups. The control groups will receive the instruction in participation in physical activity
208 currently provided by the Weight Management Program, but will receive no formal interaction
209 with an exercise instructor or physical therapist during the study period. This is the current
210 standard protocol, so no treatment is being withheld from this group of participants. One
211 intervention group will be instructed in Tai Chi exercises during weekly supervised exercise
212 sessions. A commercially available DVD will be utilized to lead the exercise session with close
213 supervision of technique and safety by the assigned researchers. Participants in this group will
214 be provided with an identical Tai Chi DVD to use during their home sessions. The DVD was
215 created by [name], a Tai Chi master who is also a medical doctor, and is specifically geared
216 towards people with arthritis who want to enjoy Tai Chi. We chose this because we could not
217 find a DVD that had been developed for people with obesity, and since many obese people
218 would also benefit from joint protection techniques, we felt that the modifications the master
219 has made for this population would be appropriate for our targeted research participants.

220 Following completion of the 8-week study period, the people who were assigned to the
221 corresponding control group will be offered a 4-week supervised Tai Chi program along with the
222 accompanying DVD. We hope that this will help provide an incentive for them to return for the
223 second measurement session, and will also reward them for participating as part of the control
224 group.

225 In the second phase of the study, a group will be instructed in an exercise program of resisted
226 exercises for trunk, upper and lower extremities and stretching exercises. These participants
227 will attend one supervised session per week and will have a DVD to use at home to remind them

228 of the exercises. This DVD will be created and produced by the researchers specifically for this

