254 instructed to walk daily for exercise, as per the current protocol. All participants will maintain
255 an exercise log to track their compliance with the home program and any additional activity they
256 perform, including walking. They will be instructed to stop exercising if they experience
257 significant shortness of breath, chest pain, dizziness, leg pain, or joint pain. They will be
258 instructed in the use of the BORG Rating of Perceived Exertion (RPE) Scale (Figure 3) with a
259 target range of 12-16. The Borg RPE Scale is a simple scale that allows an individual to quantify
260 his or her response to exercise. A rating of 12-16 encompasses a level of exercise that is rated
261 subjectively as “somewhat hard.” To increase safety in the home exercises, our participants will
262 be instructed to perform the exercises or Tai Chi forms near a support such as a chair, counter,
263 or railing that could be used for assistance in the event of a loss of balance. Participants may be
264 encouraged to discontinue the exercise and exit the study if they experience any discomfort or
265 injury as a result of participation.

266 **POTENTIAL RISKS:** There is always a risk related to falls and/or musculoskeletal injuries as a
267 result of participation in daily activity. There is an increased risk of falls associated with the Tai
268 Chi group due to the type of exercise and movement that is required with that activity. The FSST
269 was selected as a fall risk screening tool because of the similarity in activity between the FSST
270 and the Tai Chi positions. Thus people who can perform adequately on the FSST should be able
271 to safely perform the Tai Chi positions. These positions, while providing a challenge to balance,
272 should not be so difficult for participants that they will provoke a fall. Tai Chi is performed with
273 slow, controlled movements as well which will allow the participants to attend to their balance
274 as they perform the movement patterns. Additionally, all exercises (Tai Chi and resistance

275 exercises) will be performed at a supervised exercise session before a participant will be
276 performing them at home, which will allow the researchers to ensure that they are being
277 performed correctly and safely. During these exercise sessions, researchers will be present for
278 guarding to prevent falls. The exercises will be modified on an individual basis as necessary for

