306 this study may provide guidance towards improving mobility and health in people who are
307 morbidly obese.

308 **DATA COLLECTION:** Measurements will be taken on one session prior to, and on one session
309 following completion of the 8 weeks of exercise sessions. A sample data collection form is found
310 on page 31. The participant identification numbers will be the only identifying information
311 utilized during data collection and analysis. Records of the identification codes for the
312 participants will be kept by the primary investigators only, and will be stored in hard copy in
313 their locked offices, and on their password-protected computers. These codes will be stored in
314 a separate file from the research data, so that if there were a breach of the computer, the
315 identity codes would not be obvious. Any data created and collected on paper by this study will
316 be kept in the locked offices of the primary investigators. The paper data will be transferred to
317 spreadsheets on the computers of the primary investigators, which are password
318 protected. When the data are transferred to the electronic spreadsheets, only the numerical
319 codes will be used, so even if there were a breach of the computer, individual identities would
320 not be revealed. The researchers who are assigned to collect pre-test and post-test outcome

321 measures will be excluded from participation in the exercise class instruction for all groups in
322 order to maintain blinding of the researchers. The data will be analyzed using SPSS software.
323 Analysis of the test results among the test groups will include repeated measures ANOVA to
324 compare performance on the outcome measures from initiation of the exercise program to the
325 conclusion.

326 **FUNDING:** A small internal grant from Husson University will cover the cost of the DVDs and the
327 resistance equipment required for the resistance training group. No additional funding will be
328 necessary. The exercise sessions will be monitored by students who are receiving course credit
329 and therefore do not receive reimbursement for their time, and the faculty members who will
330 be present are required to carry out this research as part of their teaching loads.

331 CONSENT FORM: See attached Informed Consent Form. This form has a Fleish-Kincaid
332 readability level of 9.0. All researchers will be instructed as to how to properly administer an

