526
527 If yes, please describe
528 _____
529 _____
530
531
532 5. What prescription medications are you taking?
533
534
535
536 6. Do you use an assistive device such as a walker or a cane to help you while
537 walking?
538
539
540
541
542

543 7. How many falls have you had in the past year, approximately? _____

544

545

546 When did those falls occur? _____

547

548

549 8. How long does it take you to get from you home to Husson? _____

550

551

552

553 9. What is your primary reason for participating in this study? _____

554

555 _____

556

557

558 10. What is your occupation? _____

559

560

561

562 11. How many hours per week do you work? _____

563

564

565

566

567

568
569**Data Collection Form:**

| | Pretest |
|---|---------|
| Participant ID number: | |
| Anthropometric Data: | |
| Height | |
| Weight | |
| BMI | |
| Neck Circumference | |
| Physical Outcome Measures: | |
| FSST (Time) | |
| 6 Minute Walk test | |
| Blood Pressure | |
| Heart Rate | |
| Distance | |
| 30 Sec Sit to Stand (#) | |
| TUG Score (time) | |
| Gait Measures | |
| Gait speed | |
| Step length | |
| Step width | |
| Double limb support time | |
| Cadence | |
| Paper and pencil surveys | |
| SF-36 Score | |
| Rapid Assessment of Phys Activ | |
| Number of sessions attended at Husson | |
| Number of times exercised independently | |

570
571

572

Data Collection Form:

573

| | Post test |
|---|-----------|
| Participant ID number: | |
| Anthropometric Data: | |
| Height | |
| Weight | |
| BMI | |
| Neck Circumference | |
| Physical Outcome Measures: | |
| FSST (Time) | |
| 6 Minute Walk test | |
| Blood Pressure | |
| Heart Rate | |
| Distance | |
| 30 Sec Sit to Stand (#) | |
| TUG Score (time) | |
| Gait Measures | |
| Gait speed | |
| Step length | |
| Step width | |
| Double limb support time | |
| Cadence | |
| Paper and pencil surveys | |
| SF-36 Score | |
| Rapid Assessment of Phys Activ | |
| Number of sessions attended at Husson | |
| Number of times exercised independently | |

574

575

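### The 8-week home-exercise count has no documented place except the post-test form, so the home part of Objective 2 is likely to be missing for exercisers who do not return

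*Combined protocol and SAP*

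**What the plan says.** Objective 2 (SPECIFIC AIMS AND SCOPE) reads "Identify differences in compliance among the various types of physical activity with" "the supervised group and individual sessions". It therefore has two components, supervised classes and individual home sessions.

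The LOCATION section gives the two exercise groups one class a week for 8 weeks. Home sessions take place at home or at another location of "their choice 2 additional times per week. Participants in the control group will also attend 2" laboratory sessions, which are for testing only. The home programme is thus 2 × 8 = 16 sessions for exercisers, and controls have no study visit between the two tests.

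Under RESEARCH DESIGN, all participants keep "an exercise log to track their compliance with the home program and any additional activity they" perform. No hand-in time is stated. The Data Collection Form has the lines "Number of sessions attended at Husson" and "Number of times exercised independently". Both lines are printed on the pretest and post-test versions, but only the post-test entry can cover the intervention. DATA COLLECTION states "Measurements will be taken on one session prior to, and on one session" after the 8 weeks, and mentions no other occasion.

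PARTICIPANT RECRUITMENT AND SELECTION restricts the analysis to people who attended half or more of the supervised classes. The only analysis named is a repeated measures ANOVA of the outcome measures. No analysis of compliance and no missing-data rule is given.

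**The concern.** For most outcomes a person who does not return is a missing value. For compliance, stopping is part of what is being measured. If the home count exists only for people who come back, it is selected on the outcome, and home compliance is overstated in any group whose non-returners exercised less than its returners. If the two exercise types lose different numbers of people, the comparison between them is distorted as well. In a study that calls itself a feasibility study, the level in each group matters as much as the difference.

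The half-attendance rule adds a second selection. The text does not exempt Objective 2 from it. If it is applied there, every exerciser analysed has attended at least 4 of 8 classes, so individual supervised compliance cannot fall below 50% by construction.

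The two problems are distinct. Someone who attends 4 to 7 classes and then leaves satisfies the rule, yet has no post-test form. Removing the rule would not create that person's home count.

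**Working it through.** **Figures in the documents.** No dropout rate, expected compliance or other figure bearing on this point is stated, so there is nothing to reproduce beyond the group sizes: 3 × 15 = 45, which agrees with the planned total.

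**Route of the home count.** The log is held by the participant (RESEARCH DESIGN). It is transcribed to a line that is meaningful only at post-test (Data Collection Form). The post-test is one session after the 8 weeks (DATA COLLECTION). Weekly classes offer a chance to collect logs (LOCATION), but no section assigns that task to them. Followed as written, the plan has no step at which a non-returner's log reaches the study.

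**Illustration of size.** From the documents: 15 per group and 16 planned home sessions, so 15 × 16 = 240 possible sessions per exercise group. Assumed: returners average 12 of 16 (75%), k people do not return, and non-returners averaged m sessions.

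- All starters: [(15 − k) × 12 + k × m] / 240
- Returners only: 12/16 = 75%, whatever k is
- Overstatement: k × (12 − m) / 240

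Three values of m are shown. At two sessions a week, m = 3 is about 1.5 weeks of home exercise, mostly people the half-attendance rule would remove anyway. A person who leaves after four weekly classes would have done 4 × 2 = 8 at full home compliance, or 6 at 1.5 a week. So m = 6 to 8 is closer to someone who satisfies the rule and then leaves.

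| k | All starters, m = 3 | Overstatement, m = 3 | Overstatement, m = 6 | Overstatement, m = 8 |
|---|---|---|---|---|
| 1 | 171/240 = 71.3% | 9/240 = 3.8 points | 6/240 = 2.5 points | 4/240 = 1.7 points |
| 3 | 153/240 = 63.8% | 27/240 = 11.3 points | 18/240 = 7.5 points | 12/240 = 5.0 points |
| 5 | 135/240 = 56.3% | 45/240 = 18.8 points | 30/240 = 12.5 points | 20/240 = 8.3 points |

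**Effect on the comparison.** Suppose one exercise group loses 1 and the other 5, with equal returner means. The returner analysis shows a difference of 0. The all-starter difference is (45 − 9)/240 = 15.0 points at m = 3, (30 − 6)/240 = 10.0 at m = 6 and (20 − 4)/240 = 6.7 at m = 8. If both groups lose the same number with the same means, the between-group difference is unbiased, but each group's compliance is still overstated by the amount in the table.

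**The case against.** The strongest reply is that the plan never says the home count is gathered only at the return visit. The form is described as a sample. Its attendance line sits beside the home line, and attendance plainly accrues week by week in front of staff, so a form line shows where a total is written and not when it was collected. The consent form is not part of the text considered here and could contain an instruction about logs. This stands as a limit on certainty: capture at post-test only is an inference from the form and the schedule. It does not supply a collection step.

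A reader might go further in four ways that the documents do not support.

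- **All of Objective 2 rests on returners.** It does not. Supervised attendance can be observed for every exerciser, so non-return need not affect it if it is taken from a session register.
- **Someone who stops in week 3 is the typical case.** That person has attended at most 3 of 8 classes and is already outside the analysis under the half-attendance rule. For such people, the loss cannot be charged to log timing alone.
- **The protocol itself expects exercisers not to return.** The passage usually read that way, "accompanying DVD. We hope that this will help provide an incentive for them to return for the" second measurement, concerns controls, who have no home programme to score. No dropout rate for exercisers is given.
- **The comparison would be reversed.** Nothing in the documents shows this. The 1-versus-5 split is a chosen example.

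It is also fair to say that scoring every week after leaving class as zero is an assumption. Participants have the DVD and may continue at home.

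**Conclusion.** The point holds for the home component of Objective 2. The plan documents no way for a non-returning exerciser's home count to reach the study, and the half-attendance rule, if applied to this objective, would select the compliance analysis on compliance itself.

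The size cannot be derived from the documents. Under the assumptions above, with 1, 3 or 5 of 15 not returning, the overstatement is about 2-3, 5-8 or 8-13 points for people who leave after about half the programme. It is about 4, 11 or 19 points if non-returners did only 3 sessions, but most of those people are excluded by the attendance rule in any case. Bias in the between-group difference requires unequal loss or unequal means. Overstatement of each group's level requires only that non-returners did less than returners.

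The conclusion rests on reading the form and visit schedule as the complete collection plan. A log hand-in procedure recorded elsewhere would answer the first half of the point, but not the half-attendance rule.

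**What to change.** In DATA COLLECTION, state that the log is kept on one sheet per week. At each supervised session in the Tai Chi and resistance groups, the class leader collects or photographs it. The outcome tester should not do this, so that blinding is kept; the plan already keeps testers out of the classes. Add that staff will try to obtain the last sheet from anyone who stops, and that supervised attendance is taken from a session register. Controls have no home programme to score and can hand in their log at post-test.

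Report both components of Objective 2 for everyone who started an exercise programme, without the half-attendance filter. Give home compliance as documented sessions out of 16, with the week of stopping beside it. Count undocumented weeks as zero in the main figure, and show a sensitivity analysis that treats them as unknown, for example with bounds of none and both sessions done in each such week.

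The cost is a few minutes per existing class and a few sentences in the plan. Reported compliance will look lower, and a missed class delays that week's sheet.

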229 population, based on their knowledge of exercise. Resistance to the exercise will be achieved by
230 the use of elastic bands with varying amounts of resistance. Resistance will be increased during
231 the supervised exercise sessions, as appropriate, on an individual basis. The exercises will
232 become progressively harder over the 8-week period. An additional control group will be
233 recruited as a comparison for this resistance exercise group. The addition of a control group for
234 this phase of the study will allow the researchers to be blinded as they take measurements, and
235 will allow each phase of the study to stand on its own as a complete project with a valid
236 comparison group. After the 8-week study period is completed and post-study measurements
237 have been completed, the control group participants will be offered a 4-week supervised
238 exercise session of resistance training. As described above, this should provide incentive to
239 return for the second measurement session, and will serve as a reward for their participation.

240 All of the group exercise sessions will be supervised and led by student physical therapists, with
241 a licensed physical therapist (one of the co-investigators) present at all times. The students and
242 physical therapists are well trained in identifying and guarding patients who may be at risk for
243 falls, though the initial screening should have identified these people and allowed us to exclude
244 them from the study. Prior to starting the exercise sessions with the participants, the
245 researchers will attend instructional sessions with a local experienced Tai Chi teacher ([name]
246 [name]) to learn the correct positions and movements in order to provide effective supervision.

247 During the exercise sessions, the researchers will be observing the participants closely and
248 suggesting modifications in Tai Chi forms or resistance exercises when appropriate, according to
249 the participant's individual abilities. In this sense, the Tai Chi and the resistance exercises will be
250 tailored to the appropriate level for the individual.

251 Participants in both intervention groups will be instructed to carry out a home program twice a
252 week that is similar to what they have done in the supervised session. In addition to the group
253 and individual exercises in which two groups will participate, all study participants will be

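### The ANOVA covers some 8 to 18 outcomes with no lead outcome and no exploratory label, and the compliance objective has no named analysis and an inclusion rule that would bias it

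*Combined protocol and SAP*

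**What the plan says.** The whole visible inferential plan is one sentence under Data Collection: "Analysis of the test results among the test groups will include repeated measures ANOVA to" "compare performance on the outcome measures from initiation of the exercise program to the" conclusion. It gives no alpha, ANOVA term, lead outcome or error control.

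Specific Aims lists four objectives without ranking them: function, compliance, health measures and quality of life. The first reads "1. Identify any difference in the functional outcome measures resulting from" the different activities. The second reads "2. Identify differences in compliance among the various types of physical activity with" the group and individual sessions.

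The title calls this a feasibility study and Research Design calls it a pilot. Neither label is attached to the objectives or to the analysis.

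Participant Recruitment and Selection plans 45 people in three groups of 15. It also restricts the analysis to people who came to half or more of the supervised classes, with no exception for any objective. According to Location, controls come to the laboratory only for the two testing visits.

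**The concern.** There are two separate gaps.

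**No lead outcome.** The first objective is met by a difference on any functional measure, and the same ANOVA applies to every outcome. With many outcomes and no order among them, a nominally significant result somewhere is likely even if neither exercise program does anything. A lead outcome cannot be chosen soundly once the data have been seen. This matters because the weight-management "Program managers are seeking guidance as to successful physical activity" recommendations, so a chance finding could be passed on as advice.

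**Compliance.** It is one of four objectives, but no analysis of it is named. A pre/post ANOVA does not suit it, because class attendance accrues only during the 8 weeks. The attendance rule then selects on the very variable being compared. If one program keeps people coming and the other does not, the rule hides part of that difference.

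**Working it through.** **The plan's own figure.** 3 x 15 = 45 is consistent as arithmetic. With no alpha, power, SD or target difference stated, it cannot be reproduced as a sample-size calculation.

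**Counting outcomes** (Research Design and the data collection forms).
- Short count: TUG, 6-minute walk, sit-to-stand, FSST, gait (once), blood pressure (once), weight, SF-36 = 8.
- Long count: SPPB, TUG, 6-minute walk, sit-to-stand, FSST (5) + five gait parameters (10) + systolic and diastolic pressure (12) + heart rate, weight, BMI, neck circumference (16) + SF-36 and RAPA (18).
- SF-36 is taken as one score; subscales would raise the count.

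**Chance of at least one false positive.** With two time points, the group-by-time test is a comparison of mean change. Assumptions: two-sided 0.05 per test, all nulls true, 15 v 15, equal correlation r between the changes. I ran 100,000 simulated studies per cell.

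| Measures | r = 0.3 | r = 0.5 | r = 0.7 | Independent, 1 - 0.95^k |
|---|---|---|---|---|
| 8 | 30% | 26% | 20% | 34% |
| 12 | 40% | 32% | 24% | 46% |
| 18 | 52% | 41% | 29% | 60% |

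Smaller runs gave 19-29% for 8 measures and 27-52% for 18, a difference of no consequence. Independence is an upper bound only, because the measures overlap. A single three-group analysis (3 x 15) gives nearly the same: 24-41% for 12 measures and 30-52% for 18. Expected false positives per set are 0.05 x 8 = 0.4 to 0.05 x 18 = 0.9.

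**Effect of the attendance rule on compliance.** The documents give no attendance figures, so this is an illustration. Suppose mean attendance out of 8 is 6.0 in one group and 4.0 in the other, a true difference of 2.0, and only people with 4 or more sessions are kept.
- Binomial, p = 0.75: 63,747/65,536 = 97% are kept; their mean is 388,152/63,747 = 6.09.
- Binomial, p = 0.50: 163/256 = 64% are kept; their mean is 792/163 = 4.86.
- Observed difference: 6.09 - 4.86 = 1.23.
- With more variation between people (beta-binomial, parameters summing to 5 or 3), the difference falls to 0.97 or 0.89.

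So a true difference of 2.0 sessions would appear as about 0.9 to 1.2.

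**Power of one lead test.** At 15 v 15, 80% power needs a difference of 1.06 SD of change. The 95% CI half-width is t(0.975, 28) x sqrt(2/15) = 0.75 SD. Research Design describes two control groups, so if 15 controls are split over the phases (assumed 15 v 8), these become 1.29 and 0.91 SD.

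**The case against.** The strongest reply is that this is a small pilot that claims no significance level and tests no stated hypothesis, and family-wise error matters only if the tests are used to draw conclusions. That lowers the severity, and it is why labelling everything exploratory is an acceptable remedy. It does not remove the point, because all four objectives ask for differences or impact and nothing says that the results are descriptive.

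Three stronger readings are tempting, but the documents do not support them.

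- *The planned test is the pre/post time effect, which controls would share.* Everyone is indeed told to exercise: "and individual exercises in which two groups will participate, all study participants will be" "instructed to walk daily for exercise, as per the current protocol". But the analysis sentence compares groups, and the second control group is "recruited as a comparison for this resistance exercise group". Group-by-time is the natural reading; the plan merely leaves it unstated.
- *The plan analyses compliance with an unsuitable ANOVA.* The sentence concerns test results and is not exclusive, so another method could be used. What stands is that none is named. The pre-test form does print both compliance rows, probably carried over from a template, but supervised attendance before the first class can only be zero.
- *Logged independent exercise should be compared with controls as compliance.* Only the exercise groups are assigned a home program. Such a contrast would compare different prescriptions, not adherence.

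It is also fair to say that the error rates depend on assumed correlations and on how outcomes are counted, hence the ranges.

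**Conclusion.** The point holds in two limited parts and should be corrected; it does not invalidate the study.

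First, with no lead outcome and no exploratory label, one set of null comparisons yields a nominally significant result in roughly one study in five (8 measures, r = 0.7) to one in two (18 measures, r = 0.3). This rests on an assumed 0.05 per test, all nulls true and 15 v 15. I have not multiplied it up for two phases, because the plan does not say that they are analysed separately.

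Second, the compliance objective has no named analysis, and the attendance rule as written would bias the comparison by dropping low attenders. The direction is clear whenever one group has more of them. The size shown is illustrative only.

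**What to change.** Under Data Collection, add: *The tested effect is the group-by-time term (difference in mean change). Either one outcome already collected is named in advance as the lead outcome and all others are exploratory, or all outcomes are exploratory. Exploratory results are given as differences with 95% CIs, without significance claims.*

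Under both Participant Recruitment and Selection and Data Collection, add: *Compliance is reported for everyone who started, whatever their attendance: supervised sessions attended and home-program sessions logged, Tai Chi versus resistance, as differences with 95% CIs, noting that these groups run in different academic years. Walking logs may be described for all groups.*

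Cost: no new data, visits or software, but real choices. Non-lead outcomes lose significance claims, and so does Tai Chi versus resistance, which the Purpose names. A lead test at 15 v 15 has 80% power only for about 1.06 SD of change, so the all-exploratory option is reasonable here. If a lead test is run in each phase, the chance of at least one false positive across the two is 1 - 0.95^2 = 9.75%. Correcting every outcome instead would serve the study worse: Bonferroni over 12 to 18 measures raises the detectable difference to 1.46-1.52 SD.
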